All these previous studies were described in SWD patients working night shifts, yet approximately 3 times as many individuals work shifts that start in the early morning compared with those who work night shifts (Czeisler et al., 2009). These early-morning shift workers are a unique, high-risk group because their early work start times (3:00 AM to 6:00 AM) require the workers to wake up in the middle of the night, close to their circadian nadir, resulting in curtailed sleep and commuting to work during times of high sleepiness. Previous research has shown that early-morning shift starts in particular are associated with increased sleepiness (Knauth, 1993). To our knowledge, no studies have addressed the use of wake promoting agents for ES in early-morning shift workers.

In this clinical trial, we will test whether Solriamfetol (SUNOSITM), a drug approved for the treatment of ES in patients with obstructive sleep apnea (OSA) and narcolepsy (Schweitzer et al.,2019; Thorpy et al., 2019), is effective in: (1) decreasing sleepiness without reducing sleep duration or sleep quality; (2) improving work functioning; and (3) improving quality of life in early-morning shift workers diagnosed with ES associated with SWD.

Summary of Concept

Shift work is associated with excessive sleepiness (ES), sleep disturbances, and performance decrements due to circadian misalignment and misplacement of sleep relative to the 24-hour external environment and internal biological timing. We will test whether solriamfetol is effective in reducing excessive sleepiness without reducing sleep duration and sleep quality, thereby improving global functioning in early-morning shift workers diagnosed with ES associated with shift work disorder (SWD).

II. SPECIFIC AIMS

Hypothesis

• Excessive sleepiness during wakefulness on a workday can be improved by solriamfetol compared with placebo in patients with shift work disorder who work early-morning shifts (H_1 : $\mu_{sol} - \mu_{pl} > 0$). The statistical null hypothesis is that solriamfetol does not improve change in MWT scores versus placebo after 4 weeks of treatment (H_0 : $\mu_{sol} - \mu_{pl} \le 0$).

Primary Objective

• Demonstrate improvement of objective sleepiness (assessed with a Maintenance Wakefulness Test (MWT)) in early-morning shift workers after treatment with solriamfetol.

Secondary Objectives

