- Demonstrate improvement of subjective sleepiness [assessed with a Karolinska Sleepiness Scale (KSS, Åkerstedt & Gillberg, 1990) in early-morning shift workers after treatment with solriamfetol.
- Demonstrate improvement of clinician's global impression [assessed with Clinical Global Impression-CGI-Change (Guy, 1976)] in early-morning shift workers after treatment with solriamfetol.
- Demonstrate improvement of Patient's Global Impression of Change (Guy, 1976) after treatment with solriamfetol in early-morning shift workers.

Exploratory Objectives

- Demonstrate improvement in work function and daily activity in early-morning shift workers after treatment with solriamfetol, as assessed by Work Productivity and Activity Impairment-Specific Health Problem questionnaire (WPAI-SHP; Reilly et al., 1993; Emsellem et al., 2020).
- Demonstrate improvement in subjective global functioning, as assessed with Functional Outcomes of Sleep Questionnaire (FOSQ-10; Chasens et al., 2009) and Sheehan Disability Scale (SDS; Sheehan & Sheehan, 2008), in early-morning shift workers after treatment with solriamfetol.
- Demonstrate that early-morning shift workers who are treated with solriamfetol do not show significant reduction in objective Total Sleep Time (Actigraphy-TST) or increases in sleep disturbances (Actigraphy-Fragmentation Index).
- Demonstrate improvement of subjective sleepiness (decreased score on modified Epworth Sleepiness Scale (ESS, Johns, 1990, 1997) in early-morning shift workers after treatment with solriamfetol.

III. PARTICIPANT SELECTION

Work schedule and history. Participants must be currently employed and work 20 or more hours per week on 6-12 hour shifts. They must have a work schedule where their start times are between 3am and 7am at least three days per week, and have worked early morning start shifts for at least three months prior to the study.

Participants must show evidence for SWD, either by prior diagnosis or via screening questionnaires (4-item SWD screening questionnaire, modified ESS) followed by SWD confirmation by a clinician.

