- 24-h actigraphy to assess sleep duration and sleep quality

At baseline and End of Treatment visits (visit 1 & 5):

- Objective sleepiness (MWT)
- Subjective sleepiness (KSS, ESS)
- Clinical global impression (CGI, CGI-S, CGI-C)
- Patient global impression (PGI, PGI-S, PGI-C)
- Work function and daily activity (WPAI-SHP)
- Subjective global functioning (FOSQ-10, SDS)

Analysis of objective sleepiness.

The **Primary Endpoint** of this study is the change in objective sleepiness between the Baseline MWT and the End of Treatment (EOT) MWT [average sleep latency on first 4 scheduled naps]. To test the primary hypothesis, the primary endpoint of the change in MWT from Baseline to EOT between the solriamfetol group and the placebo group will be analyzed using a mixed model repeated measures analysis that will include Baseline MWT, treatment (solriamfetol, placebo), time (as a discrete factor), and treatment by time interaction as fixed effects and participant as a random effect. An unstructured variance-covariance matrix will be used to model the correlation among repeated measurements. The degrees of freedom will be estimated by the Kenward-Roger approximation method. A 2-sided 95% confidence interval (CI) of the mean difference in MWT from Baseline to EOT between solriamfetol and placebo will be constructed.

Analysis of subjective sleepiness and clinical condition.

The **Secondary Endpoints** are:

- a) the change in subjective sleepiness between the Baseline KSS and the EOT KSS [average of the KSS given before the first 4 scheduled naps]
- b) the change in clinical condition between Baseline and EOT as assessed by a physician using the CGI-C.
- c) the change in the patient's subjective report between Baseline and EOT visit as assessed by PGI-C.

To test the secondary objectives, the secondary endpoint of the change in KSS from Baseline to EOT between the solriamfetol group and the placebo group will be analyzed using a mixed model repeated measures analysis that will include Baseline KSS, treatment (solriamfetol, placebo), time (as a discrete factor), and treatment by time interaction as fixed effects and participant as a random effect. An unstructured variance-covariance matrix will be used to model the correlation among repeated measurements. The degrees of freedom will be estimated by the Kenward-Roger approximation method. A 2-sided 95% CI of the mean difference in KSS from Baseline to EOT between solriamfetol and placebo will be constructed.

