For the secondary endpoints of CGI and PGI, change between the treatment group and the placebo group will be analyzed using a chi-square test.

To address the multiplicity issue due to the hypothesis testing on the primary and secondary endpoints, a fixed hierarchical testing sequence will be employed. The familywise type I error rate will be controlled at the 2-sided significance level of 0.05. The testing procedure will be stopped when the p-value of a specific endpoint exceeds the significance level of 0.05. Statistical hypotheses will be tested in the following sequential order:

- 1. the change in objective sleepiness between the Baseline MWT and the End of Treatment (EOT) MWT
- 2. the change in subjective sleepiness between the Baseline KSS and the EOT KSS
- 3. the change in clinical condition between Baseline and EOT as assessed by a physician using the CGI-C
- 4. the change in the patient's subjective report between Baseline and EOT visit as assessed by PGI-C.

The **Exploratory Endpoints** are:

- a) the change in subjective sleepiness between Baseline and EOT visit as assessed by modified ESS.
- b) the change in work function and daily activity between Baseline and EOT visit as assessed by WPAI-SHP
- c) the change in subjective global functioning between Baseline and EOT visit as assessed with FOSQ-10 and SDS.
- d) no change in objective sleep duration or sleep quality assessed by actigraphy-estimated TST and actigraphy-estimated FI, averaged across the 2 Baseline weeks compared to weeks 3+4 of Treatment.

To test the exploratory objectives, we will analyze the change from Baseline to EOT between the solriamfetol group and the placebo group by descriptive statistics, and to analyze the continuous variables using a mixed model with repeated measures analysis that will include baseline measure, treatment (solriamfetol, placebo), time (Baseline, EOT), and treatment by time interaction as fixed effects and participant as a random effect, and to analyze discrete variables using a chi-square test.

All significance tests will be 2-tailed and at p < 0.05 level.

Sample Size Justification

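### The exploratory sleep objective claims no loss of sleep, but the only inferential analysis is a difference test with no margin or confidence-interval criterion

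*Combined protocol and SAP*

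**What the plan says.** Section II (Specific Aims, Exploratory Objectives) includes this aim: "Demonstrate that early-morning shift workers who are treated with solriamfetol do not show significant reduction in objective Total Sleep Time". The same sentence extends it to increased sleep disturbance, measured by the actigraphy FI. In section V.b (Biostatistical Analysis), item d of the Exploratory Endpoints words the endpoint as "no change in objective sleep duration or sleep quality", with TST and FI "averaged across the 2 Baseline weeks compared to weeks 3+4 of Treatment".

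The analysis paragraph that follows covers all exploratory endpoints together: "we will analyze the change from Baseline to EOT between the solriamfetol group and the placebo group". It uses descriptive statistics and, for continuous variables, a mixed model with the baseline measure, treatment, "time (Baseline, EOT), and treatment by time interaction as fixed effects and participant as a random effect". The general rule is: "All significance tests will be 2-tailed and at p < 0.05 level".

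For the primary Maintenance of Wakefulness Test (MWT) endpoint and the Karolinska Sleepiness Scale (KSS), section V.b also commits to an interval. For the KSS it reads: "A 2-sided 95% CI of the mean difference in KSS from Baseline to EOT between solriamfetol and placebo will be constructed". There is no such commitment for TST or FI. The Sample Size Justification covers the MWT, the KSS and the CGI-C, but not TST or FI.

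**The concern.** The improvement endpoints ask whether there is a difference, and a difference test answers that. The TST and FI endpoint asks whether a difference is absent, yet it is given the same test. An objective phrased as showing no significant reduction, paired with a two-sided test at 0.05 and no other criterion, invites a reader to take p > 0.05 as success. Noisier actigraphy or more missing data would then make success easier.

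What is at stake is one statement in the trial report. It is a prominent one: section I gives the first aim as "decreasing sleepiness without reducing sleep duration or sleep quality", and the Summary of Concept repeats the idea. Section VI lists insomnia among the most common adverse reactions, so an effect on sleep is plausible. A no-sleep-loss statement could be made while the data remained compatible with a loss.

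**Working it through.** **Inputs from the protocol.** Sample Size Justification: 50 participants per group, alpha 0.05, MWT difference 5.7 minutes, SD 7.2, stated power 97%. Section V.b: two-sided tests at 0.05. No SD or margin is given for TST or FI, so results are in units of the SD of change (d). Values in minutes rest on assumed SDs.

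**Step 1: reproduce the plan's own figure.** Standard error = 7.2 × √(2/50) = 7.2 × 0.2 = 1.44 minutes. Standardised effect = 5.7/1.44 = 3.96. Normal approximation: Φ(3.96 − 1.96) = 97.7%. Noncentral t with 98 df: 97.5%. The stated 97% is reproduced, so 50 per arm with this method is a sound basis.

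**Step 2: chance that a real loss is non-significant.** For a two-sample comparison of change with n = 50 per arm, df = 98 and noncentrality = d × √(50/2) = 5d. The chance of p > 0.05 is the probability that a noncentral t lies between −1.984 and +1.984.

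| True loss (SD of change) | Noncentrality | Chance of p > 0.05 |
|---|---|---|
| 0.2 | 1.0 | 83% |
| 0.3 | 1.5 | 68% |
| 0.4 | 2.0 | 49% |
| 0.5 | 2.5 | 30% |

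The loss detected with 80% probability is about 0.57 SD.

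**Step 3: precision.** 95% CI half-width = t(0.975, 98) × √(2/50) = 1.984 × 0.2 = 0.397 SD. With 45 or 55 per arm it is 0.42 or 0.38 SD. In the extreme case of a loss that just misses significance, the interval reaches 2 × 0.397 = 0.79 SD.

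**Step 4: minutes of TST, under assumed SDs of change.**
- SD 30: 0.397 × 30 = 11.9 minutes.
- SD 45: 0.397 × 45 = 17.9 minutes.
- SD 60: 0.397 × 60 = 23.8 minutes.

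**Step 5: does the stated model change this?** With complete data, the treatment-by-time estimate from a model with these terms equals the simple difference in mean change; 60 simulated datasets confirmed this. The model's own standard error averaged 2% to 9% smaller. That would put the half-width at 0.397 × 0.98 = 0.39 down to 0.397 × 0.91 = 0.36 SD, which does not alter the conclusion.

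**Step 6: what a margin would require.** With a true difference of zero and one-sided alpha 0.025, the smallest margin with 80% power at 50 per arm is (1.960 + 0.842) × 0.2 = 0.56 SD.

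**The case against.** The best defence is that this is the last of four exploratory items, outside the fixed testing sequence and the sample size. Formal margins are not usually expected there. Descriptive statistics are planned as well, and the planned model can yield the needed interval. All of this stands, and it limits the consequence. It does not turn non-significance into evidence of no effect, and the descriptive statistics supply no criterion for the claim.

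A reader might infer more than the documents support in four ways.

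- **That p > 0.05 is a written success rule.** It is not. It is the natural reading of the objective in the absence of any other criterion, so the harm is a possible reporting choice and not a planned decision.
- **That the contrast is undefined, or is a within-arm test.** The objective mentions only treated workers, but so do the primary and secondary objectives, and the MWT and KSS are analysed between groups. Section V.b names the between-group change, with a treatment-by-time term, for every exploratory endpoint.
- **That the time windows conflict.** Item d specifies the actigraphy windows, and these fill in the generic Baseline and EOT labels. Weeks 3 and 4 are the final treatment segment, which ends at Visit 5.
- **That the trial's main conclusions are weakened.** The primary and secondary analyses and the control of type I error do not depend on TST or FI.

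The values in minutes do rest on SDs from outside the documents, and no document figure shows whether that precision is adequate. The argument does not need them.

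**Conclusion.** The concern holds as a mismatch between the claim and the analysis. The plan aims to demonstrate absence of sleep loss, but provides only a difference test and descriptive statistics, with no margin or interval criterion for TST or FI. At 50 per arm the test would miss a true loss of 0.4 SD about half the time, and the 95% CI would extend about 0.40 SD either side of the estimate. These figures assume 50 analysable participants in each arm, a simple comparison of change and approximate normality. In SD units they apply equally to an increase in FI.

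The point is worth acting on because the statement belongs to the trial's first stated aim and the correction is nearly free. It is not a threat to the primary or secondary results.

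**What to change.** In the exploratory objective in section II and in item d of the Exploratory Endpoints in section V.b, replace the language of demonstration and no change with estimation: *estimate the solriamfetol-placebo difference in change in TST and FI (2 Baseline weeks versus treatment weeks 3+4), with two-sided 95% CIs*. Add one sentence saying that no reduction or no change will not be concluded from p > 0.05. If a no-reduction claim is wanted, justify margins for TST and FI before unblinding, and make the claim only when the CI excludes them. The documents offer no basis for a margin, so none is proposed here.

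The cost is wording in two places and one reported interval per measure, from a model already planned. No new data or larger sample is needed, and the endpoint stays exploratory. The downside is that the no-sleep-loss statement may have to be reported as inconclusive, and any margin would need support from outside these documents.

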Medication/drug use. Participants must report no current or recent (within 2 years) history of drug or alcohol dependency, or treatment for drug or alcohol dependency. They must report moderate or no use of caffeine, cigarettes or other nicotine-containing products, cannabis/marijuana, and alcohol by history; and be willing to abstain from products containing cannabis/marijuana for the duration of the screening and while in the study. A positive test for cannabinoid (THC) at screening may be repeated once and if negative the participant will be allowed to enter the study. Participants will be urine drug tested during screening and any positive test for opiates, phencyclidine, cocaine, amphetamines (unless prescribed), or alcohol at screening will be exclusionary.

Participants must report no use of a monoamine oxidase inhibitor (MAOI) in the past 14 days (or five half-lives, whichever is longer) prior to the Baseline Visit, and must not plan to use an MAOI during the study.

Participants must report no use of any investigational drug in the 30 days (or 5 half-lives, whichever is longer) prior to the Baseline visit, and have no plans to use any investigational drug (other than the study drug) during the study.

Participants must report no use of any over-the-counter (OTC) or prescription medication that could affect the evaluation of excessive daytime sleepiness within a time period prior to the Baseline visit corresponding to at least 5 half-lives of the drug(s). Participants must also not plan to use such drug(s) at any point throughout the duration of the study. Examples of excluded medications include OTC sleep aids, stimulants (e.g. methylphenidate, amphetamines, modafinil, and armodafinil), sodium oxybate, pemoline, pitolisant, bupropion, trazodone, vortioxetine, duloxetine, tricyclic antidepressants, hypnotics, benzodiazepines, barbiturates, and opioids.

Participants must report no previous exposure to solriamfetol (JZP-110, ADX-N05, R228060, or YKP-10A).

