- 7. History of bariatric surgery within the past year or a history of any gastric bypass procedure.
- 8. Use of an MAOI in the past 14 days or five half-lives (whichever is longer) prior to the Baseline Visit, or plans to use an MAOI during the study.
- 9. Pregnant or intention to become pregnant.
- 10. Breast-feeding or plans to breastfeed.
- 11. On long-term sick leave or with no history of work in the last 12 months
- 12. Diagnosis with sleep disorder (regardless of treatment status) other than SWD including: OSA, PLMD, other circadian rhythm sleep disorders, narcolepsy, or RLS determined by a previous sleep-lab diagnosis or during the home sleep test.
- 13. History of excessive caffeine use or anticipated excessive use (>600mg/day) during the study.
- 14. Use of any OTC or prescription medications that could affect the evaluation of EDS within a time period prior to the Baseline visit corresponding to at least 5 half-lives of the drug(s) or planned use of such drug(s) at some point throughout the duration of the treatment period. Examples of excluded medications include OTC sleep aids, stimulants (e.g. methylphenidate, amphetamines, modafinil, and armodafinil), sodium oxybate, pemoline, pitolisant, bupropion, trazodone, vortioxetine, duloxetine, tricyclic antidepressants, hypnotics, benzodiazepines, barbiturates, and opioids.

- 15. Received an investigational drug in the past 30 days or 5 half-lives (whichever is longer) prior to the Baseline visit or plans to use an investigational drug (other than the study drug) during the study.
- 16. History or presence of bipolar disorder, bipolar-related disorders, schizophrenia, schizophrenia spectrum disorders, or other psychotic disorders according to DSM-5 criteria.
- 17. Current or recent (within the past 2 years) diagnosis of a moderate or severe substance use disorder (excluding caffeine) according to DSM-5 criteria. Nicotine use disorder is exclusionary only if it has an effect on sleep (i.e., a participant who routinely awakens at night to smoke) or will interfere with study compliance.
- 18. Current, recent (within the past 2 years), or seeking treatment for a substance-related disorder.
- 19. Positive urine drug screen (UDS) for opiates, phencyclidine (PCP), cocaine, cannabinoid (THC), or amphetamines at Screening or at any point throughout the duration of the study, except for a prescribed drug (e.g., amphetamine) at Screening.

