- 20. History of regular heavy use of tetrahydrocannabinol containing products. Recreational users of cannabis may be repeat UDS tested once during the Screening period. If this is negative, the participant may be allowed to enter the study.
- 21. Positive alcohol test at Screening. Binge drinking (5 or more drinks per day for men, 4 or more drinks per day for women) within the past month.
- 22. History of PKU or history of hypersensitivity to phenylalanine-derived products.
- 23. Previous exposure to solriamfetol (JZP-110, ADX-N05, R228060, or YKP-10A).

Inclusion of racial/ethnic minorities. Our recruitment procedures will provide all applicants with an equal opportunity to participate in our studies regardless of race, ethnicity, or national origin.

Sex. We will attempt to include equal numbers of women and men in the proposed study.

Source of participants and recruitment methods:

We will recruit early-morning shift workers who work a fixed work schedule, where work times start between 3 AM-7 AM at least 3 days per week. We may use a participant recruitment company to pre-screen individuals for eligibility to the study. We will recruit participants through internet, radio, and newspaper advertising, RSVP, Rally, and social media notices. We will also use snowball sampling where participants may notify their coworkers. We will recruit among all occupations, and include participants within approximately a 1-2 hours distance from BWH.

We plan to screen up to 500 people, randomize 110 people in order to obtain 100 who meet all criteria and complete the study.

Screening questionnaires

The following questionnaires/instruments will be administered during the screening process in order to collect information necessary for determining inclusion/exclusion criteria or to meet regulatory requirements [see Appendix I for copies of each questionnaire]:

At phone/ online (REDCap) screening:

Shiftwork Disorder screening instrument, a 4 item questionnaire

Modified Epworth Sleepiness Scale, an 8-item questionnaire that rates the probability of falling asleep in different situations [scores <11 will be exclusionary]

At Screening Visit:

- 1. Subject Information questionnaire [used to collect medical, sleep-wake, and work history]
- 2. Personal Data (race/ethnicity) form
- 3. BDI II [scores > 19 indicating moderate or severe levels of depression will be exclusionary]
- 4. BAI [scores >35 indicating high anxiety levels will be exclusionary]

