- Baseline Visit 2: Maintenance of Wakefulness Test (MWT; Littner et al., 2005). The potential participant will report to the Center for Clinical Investigation (CCI) at BWH approximately one hour after their usual wake time (UW) on early morning start days. The participant will have their vitals taken and then be instrumented for polysomnography (PSG) and a 40-min MWT will be carried out at UW+ ~2, 4, 6, and 8 hours. Five minutes prior to each nap, a KSS will be administered. In between MWTs, the participant will complete baseline questionnaires [Chronotype questionnaire for Shift-Workers (MCTQ shift, Juda et al., 2013), WPAI-SHP, FOSQ-10, SDS, modified ESS]. A physician will evaluate the participant on the CGI Severity of Illness scale and the participant will self-report on Patient's GI Severity of Illness scale. A breakfast and lunch will be served between MWTs, shortly after the end of a nap. If daytime sleepiness is confirmed (average sleep latency of <20 min on the four MWT naps), the participant is considered to meet the inclusion criteria and the study can start. The participant will take home a wrist activity monitor to wear 24/7, and will be instructed to complete an electronic daily diary containing questions related to wake and sleep patterns. This visit is expected to take 10 hours.
- **Baseline Segment**: Two weeks of activity monitoring and daily completion of a sleep and work diary. Daily sleep surveys will be administered prior to starting work and daily work diaries will be administered after work at participant-selected times and will be sent to participants via email or via text message using Twilio, or provided in a hard-copy binder.
- Randomization Visit 3: The participant will have their wrist activity monitor downloaded and reinitialized, vital signs will be recorded, they will be asked about their symptoms and about any adverse events, and have the C-SSRS-since-last-visit reviewed with them, and female participants will have a urine pregnancy test. If no exclusionary criteria are identified, the participant will be randomized and given their first 2 weeks of study medication.

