Participants will take the BDI and those who indicate suicidal thoughts (score of 1 or greater on question 9) and/or indicate moderate or severe depression (total score of 19 or greater) will be excluded. Responses to the BDI will be reviewed before the participant leaves the Screening Visit. Those who have indicated suicidal thoughts will be immediately referred to a clinical psychologist, a psychiatrist, or other clinician for appropriate assessment and triage. All other participants and their responses to the BDI will be evaluated by a licensed physician to exclude those with a history of suicidal thoughts or substance abuse disorder.

Current suicide risk will be assessed via the C-SSRS. "Baseline/Screening" version of the C-SSRS will be used at Visit 1. "Since Last Visit" version of the C-SSRS will be used at visits 3, 4, 5, and 6. Responses to the C-SSRS will be reviewed before the participant completes the visit. Participants who indicate a positive response to item number 4 and/or number 5 on the C-SSRS will be immediately referred to a clinical psychologist, a psychiatrist, or other clinician for appropriate assessment and triage. They will be excluded from further participation in the study. In addition, any spontaneous expression of suicidality will be immediately referred to a clinician for appropriate assessment and triage.

Safety and tolerability assessments throughout the study will include weekly queries for adverse events. After two weeks of treatment, an in-person visit to evaluate vital signs and AEs will be conducted. After four weeks of treatment, a PE including vital signs, EKG, UA, CBC, and a metabolic panel will be conducted. Approximately one week after completion of the study, a final safety visit is scheduled. This will include a PE, vital signs, symptoms, AEs, and C-SSRS change.

In order to minimize the safety risks associated with inadequate sleep, the participant will not be allowed to drive to and from the MWT visits.

All participants who withdraw from the study will be asked to come in for a final Safety Visit. If participants withdraw after more than one week in the treatment phase of the study, they will be asked to come in for a MWT visit.

Population pharmacokinetic analysis indicated that age, gender, and race do not have clinically relevant effects on the pharmacokinetics of solriamfetol.

Outcomes monitoring

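### The BDI-II exclusion limit is stated in two incompatible ways, so a participant scoring exactly 19 is both eligible and excluded

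*Combined protocol and SAP*

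**What the plan says.** Two current parts of the combined protocol and SAP give a scored depression limit for entry.

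- Section III, Screening questionnaires, At Screening Visit, item 3 (BDI II): "scores > 19 indicating moderate or severe levels of depression will be exclusionary".
- Section VIII, Safety monitoring: participants who "indicate moderate or severe depression (total score of 19 or greater) will be excluded". The same sentence separately excludes anyone who endorses suicidal thoughts on question 9.

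The surrounding text does not choose between them. The numbered Exclusion Criteria in Section III contain no BDI score. The paragraph on psychiatric and psychological suitability names the BDI as a screening tool but gives no number. Section V schedules the BDI at Screening Visit 1, and Appendix I lists only the BDI-II, at that visit. At Randomization Visit 3 the rule is general: "If no exclusionary criteria are identified, the participant will be randomized".

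**The concern.** An eligibility threshold should give the same answer whoever applies it. Here, staff working from the Section III list would admit a participant scoring 19, and staff working from Section VIII would exclude the same person. Either decision departs from one part of the protocol.

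The limit is a psychiatric safety exclusion. Section VI warns that a stimulant or wake-promoting drug could worsen existing affective disorders, and the BDI limit is one of the ways the plan keeps such people out. What is at stake is consistent application of that safeguard and a clean eligibility record. The primary analysis is not affected.

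**Working it through.** **The two rules over integer scores**

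| Source | Rule | Lowest excluded score | Score of 18 | Score of 19 | Score of 20 |
|---|---|---|---|---|---|
| Section III, Screening questionnaires | > 19 | 20 | eligible | eligible | excluded |
| Section VIII, Safety monitoring | ≥ 19 | 19 | eligible | excluded | excluded |

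The rules agree at every score except 19.

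**Could they be two different rules on purpose?**

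- Instrument: Section III says BDI II and Section VIII says BDI, but Appendix I lists only the BDI-II, so there is one form.
- Visit: both apply at the Screening Visit.
- Label: both describe the excluded range as moderate or severe depression, so they are meant to mark the same boundary.
- Comparison: the anxiety limit (BAI) is above 35 in both Section III and Section VIII. Nothing suggests that the safety section was meant to be stricter than the screening list.
- Status: both are current text. Neither comes from a summary of changes.

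This is an inconsistency, not a two-tier design.

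**Size**

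The recruitment text in Section III gives the base: "We plan to screen up to 500 people, randomize 110 people". The documents do not say how many people score exactly 19, so the share p is assumed to lie between 0.5% and 2%.

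Expected number randomised with a score of 19, if the looser rule is applied = 110 × p:

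- p = 0.5%: 110 × 0.005 = 0.55
- p = 2%: 110 × 0.02 = 2.2

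That is about 0.6 to 2 people. The plan states no figure of its own to reproduce here, and no sample size, power or alpha figure depends on the limit.

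**The case against.** The best reply is that exclusions are cumulative. Staff who apply both sections would exclude a 19, so the stricter rule wins in practice, and a 19 is randomised only if Section VIII is overlooked. Section VIII also has BDI forms checked before the participant leaves the visit, and for those who do not report suicidal thoughts, "their responses to the BDI will be evaluated by a licensed physician". A score of 19 would therefore be seen by a clinician.

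This stands as a reason to call the impact low. It does not remove the conflict. The physician review is not told which limit to use, and its stated purpose is to find a history of suicidal thoughts or substance abuse, not to settle the cut-off. Reading the two rules together to get 19 or greater is sensible, but the protocol does not say to do so, and Section III on its face admits a 19.

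A reader might also infer a larger problem in two ways.

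- **That the conflict touches everyone screened.** Applying 2% to 500 would give 500 × 0.02 = 10 people. But the screening process begins by phone or online, and the BDI is taken only at Visit 1, so some of the 500 may never complete it. Others who do would fail on different criteria.
- **That the BDI-II and BAI should be repeated in anyone who stops a psychotropic drug after Visit 1.** The medication washout is counted back from the Baseline Visit, and exclusion 19 tolerates a positive urine screen "except for a prescribed drug (e.g., amphetamine) at Screening". But that example concerns one urine test. No text describes stopping an antidepressant or benzodiazepine after Visit 1, none says that an excluded drug lowers these scores, and the number affected may be zero. Exclusion 1 and the Visit 3 review of symptoms, adverse events and C-SSRS already allow such a person to be excluded. The documents do not support a finding here.

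**Conclusion.** The inconsistency is confirmed. The protocol gives two limits for the same form at the same visit under the same label, and they disagree at a score of exactly 19. Which one was intended cannot be settled from the documents.

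The impact is low: one score, only among people who reach Visit 1, and about 0.6 to 2 of the 110 randomised. That range rests wholly on the assumed 0.5% to 2%. The textual conflict rests on no assumption. It should still be corrected, because it is a decision threshold for psychiatric safety and the correction costs almost nothing.

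**What to change.** State one BDI-II limit in both Section III (Screening questionnaires, At Screening Visit, item 3) and Section VIII (Safety monitoring). Unless the sponsor confirms that the other was intended, use a total score of 19 or greater, the more cautious of the two already in the text. In that case only Section III changes. If the sponsor confirms that scores above 19 were intended, only Section VIII changes. Leave the BAI limit at above 35, since it already agrees in both places.

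The cost is one corrected threshold. With 19 or greater, the downside is that the few people who score exactly 19 are not enrolled. No change to the visit schedule, the sample size or the analysis is needed.
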